3.1.1 Trial Design Diagram

*Patients from parent trial who were on placebo

**Patients from parent trial who were on active medication

1. PK / Efficacy Analysis at [redacted]. An increase in dose to [redacted] every [redacted] weeks if needed at [redacted]. Refer to Table 3.1: 1.

V = Study Visit
 W = Week (study weeks)
 FUP = Follow Up
 EoT = End-of-Treatment
 EoS = End-of-Study
 REP – Residual Effect Period

3.2 DISCUSSION OF TRIAL DESIGN, INCLUDING THE CHOICE OF CONTROL GROUP(S)

This trial will be conducted as a prospective, open-label design. The aim of the trial is to allow treatment continuation to individual patients who completed the 1368-0052 PoCC trial and evaluate the sustainability of response. Additionally, this trial provides opportunity for the patients who were on the placebo arm in the 1368-0052 PoCC trial to get access to the trial treatment. It is also designed to generate additional safety information.

Patients who prematurely discontinued the 1368-0052 PoCC trial are not eligible to participate in this study. For patients who terminate study drug prematurely in this extension study the subsequent visit will be replaced by an early EoT visit followed by an end of study (EoS) visit 16 weeks after the last study drug administration.

Interim analyses of PK, ADA, and clinical data may be performed throughout the conduct phase of this 2-year trial to support future trial applications, IB, regulatory documents and scientific publications. The final analysis of the entire trial data will start once the last patient has completed the EOT visit and final report will include all trial data. Individual patient participation is concluded when the patient has completed the last scheduled visit. The end of whole study is defined as “last patient out”; i.e., last scheduled visit completed by the last patient in the study. All the parameters will be assessed in a descriptive manner, since the trial is open-label.

An independent DMC will evaluate safety and efficacy data on a continuous basis.

3.3 SELECTION OF TRIAL POPULATION

Patients in this long-term open label extension (OLE) trial will be rolled over from the 1368-0052 PoCC trial. The total number of patients to be rolled over depends on how many eligible patients roll over from the 1368-0052 PoCC trial. The maximum number of patients eligible to rollover is approximately 45 from multiple countries and multiple sites. This OLE study aims to offer active long-term treatment to patients having completed treatment with spesolimab in the 1368-0052 PoCC trial, and an opportunity for patients on the placebo arm to get active treatment. This study will also help to characterize the safety and clinical outcome of spesolimab long-term treatment.

A log of all patients enrolled into the trial (i.e. who have signed informed consent) will be maintained in the ISF irrespective of whether they have been treated with investigational drug or not. If a patient is enrolled in error (does not meet all inclusion criteria or meets one or more exclusion criteria on the day of enrolment), the sponsor should be contacted immediately.

3.3.1 Main diagnosis for trial entry

Patients with HS who have completed the treatment with spesolimab in the parent HS trial.

Please refer to [Section 8.3.1](#) (Source Documents) for the documentation requirements pertaining to the in- and exclusion criteria.

3.3.2 Inclusion criteria

1. Patients who have completed treatment in the parent HS spesolimab trial (1368-0052) without premature discontinuation.
2. Signed and dated written informed consent in accordance with ICH Harmonized Guideline for Good Clinical Practice (ICH-GCP) and local legislation prior to admission to the trial.
3. WOCBP¹ must be ready and able to use highly effective methods of birth control per ICH M3 (R2) that result in a low failure rate of less than 1% per year when used consistently and correctly. A list of contraception methods meeting these criteria is provided in the patient information and consent form and in [Section 4.2.2.7](#).

3.3.3 Exclusion criteria

1. Women who are pregnant, nursing, or who plan to become pregnant while in the trial.
2. Patients who experienced study treatment-limiting adverse events during the 1368-0052 parent trial.

¹ A woman is considered of childbearing potential (WOCBP), i.e. fertile, following menarche and until becoming postmenopausal unless permanently sterile. Permanent sterilisation methods include hysterectomy, bilateral salpingectomy and bilateral oophorectomy. Tubal ligation is NOT a method of permanent sterilisation. A postmenopausal state is defined as no menses for 12 months without an alternative medical cause.

3. Severe, progressive, or uncontrolled condition such as renal, hepatic, haematological, endocrine, pulmonary, cardiac, neurologic, cerebral, or psychiatric disease, or signs and symptoms thereof.
4. Any new documented active or suspected malignancy except appropriately treated basal cell carcinoma, squamous cell carcinoma of the skin or in situ carcinoma of uterine cervix.
5. Use of any restricted medication or any drug considered by the investigator likely to interfere with the safe conduct of the study since the last visit of the 1368-0052 parent trial.
6. History of allergy/hypersensitivity to the systemically administered trial medication agent or its excipients.
7. Major surgery (major according to the investigator's assessment) planned during this extension trial (e.g. hip replacement, aneurysm removal, stomach ligation), as assessed by the investigator.
8. Any condition which in the opinion of the investigator affects the safety of the patient, the patient's ability to participate in this trial or could compromise the quality of data.
9. Any suicidal behaviour in the past 2 years (i.e. actual attempt, interrupted attempt, aborted attempt, or preparatory acts or behaviour).
10. Any suicidal ideation of type 4 or 5 on the C-SSRS in the past 3 months (i.e. active suicidal thoughts with method and intent but without specific plan, or active suicidal thoughts with method, intent and plan).
11. Currently enrolled in another investigational device or drug trial, except for 1368-0052.
12. Previous participation in this trial.

3.3.4 Withdrawal of patients from treatment or assessments

Patients may discontinue trial treatment or withdraw consent to trial participation as a whole ("withdrawal of consent") with very different implications; please see [Sections 3.3.4.1](#) and [3.3.4.2](#) below. Every effort should be made to keep the patients in the trial: if possible on treatment, or at least to collect important trial data. Measures to control the withdrawal rate include careful patient selection, appropriate explanation of the trial requirements and procedures prior to trial enrolment, as well as the explanation of the consequences of withdrawal. The decision to discontinue trial treatment or withdraw consent to trial participation and the reason must be documented in the patient files and Case Report Form (CRF). If applicable, consider the requirements for Adverse Event collection reporting (please see [Sections 5.2.6.2.1](#) and [5.2.6.2](#)).

Patients withdrawn from the trial, independent of the underlying reason, should undergo the EoT visit as soon as possible, the FUP 1 Visit two weeks after the last dose, and the EoS Visit 16 weeks after the last dose for safety reasons. This should also be proposed to patients who withdraw their informed consent.

3.3.4.1 Discontinuation of trial treatment

An individual patient will discontinue trial treatment if:

- The patient wants to discontinue trial treatment, without the need to justify the decision.
- The patient has repeatedly shown to be non-compliant with important trial procedures and, in the opinion of both, the investigator and sponsor representative, is not willing or able to adhere to the trial requirements in the future.

- The patient develops infections such as HIV, viral hepatitis or tuberculosis. However, if latent tuberculosis is diagnosed during the trial, patients can receive anti-tuberculosis treatment as per investigator discretion and continue receiving study medication as per investigator. Refer to [Section 6.2.1.2](#)
- The patient needs to take concomitant medication such as immunosuppressive biologics, live vaccines, or other concomitant medication that interferes with the Investigational Medicinal Products (IMP) or other trial treatment. Also refer to [Sections 4.2.1](#) and [4.2.2](#).
- The patient can no longer receive trial treatment for medical reasons such as surgery, serious or severe Drug Induced Liver Injury attributable to the trial drug, other adverse events, other diseases, or pregnancy. Also refer to [Sections 5.2.6.1.4](#) and [5.2.6.2.3](#).
- The patient develops suicidal ideation of type 4 or 5 in the C-SSRS (i.e. active suicidal thoughts with method and intent but without specific plan, or active suicidal thoughts with method, intent and plan) or any suicidal behaviour (i.e. actual attempt, interrupted attempt, aborted attempt, or preparatory acts or behaviour). The patient should immediately be referred to a mental health professional for further work-up.
- The patient is a Non-responder on 1200 mg of IMP and there is no change or no improvement in their HS-PGA grade at Week 24 compared to Week 12.

In addition, the principal investigator may discontinue subjects at any time based on his or her clinical judgment.

For individual stopping rules related to specific AEs, please see [Section 4.2.1](#).

In case of a temporary reason, trial treatment should be restarted if medically justified, please see [Section 4.1.4](#).

For all patients the reason for withdrawal from trial treatment (e.g. adverse events) must be recorded in the CRF. This data will be included in the trial database and reported.

If new efficacy/safety information becomes available, BI will review the benefit-risk-assessment and, if needed, pause or discontinue the trial treatment for all patients or take any other appropriate action to guarantee the safety of the trial patients.

Even if the trial treatment is discontinued, the patients remain in the trial and, given their agreement, will undergo the procedures for early treatment discontinuation and follow-up as outlined in the [Flow Chart](#) and [Section 6.2.3](#).

3.3.4.2 Withdrawal of consent to trial participation

Patients may withdraw their consent to trial participation at any time without the need to justify the decision. If a patient wants to withdraw consent, the investigator should be involved in the discussion with the patient and explain the difference between trial treatment discontinuation and withdrawal of consent to trial participation, as well as explain the options for continued follow-up after trial treatment discontinuation, please see [Section 3.3.4.1](#) above.

3.3.4.3 Discontinuation of the trial by the sponsor

BI reserves the right to discontinue the trial overall or at a particular trial site at any time for the following reasons:

1. Failure to meet expected enrolment goals overall or at a particular trial site.
2. New efficacy or safety information invalidating the earlier positive benefit-risk-assessment, please see [Section 3.3.4.1](#).
3. Deviations from ICH-GCP, the trial protocol, or the contract impairing the appropriate conduct of the trial.

Further follow up of patients affected will occur as described in [Section 3.3.4.1](#). The investigator / the trial site will be reimbursed for reasonable expenses incurred in case of trial termination (except in case of the third reason).

4. TREATMENTS

4.1 INVESTIGATIONAL TREATMENTS

4.1.1 Identity of the Investigational Medicinal Products

Table 4.1.1: 1 Test product 1 – BI 655130 (spesolimab) solution for injection

Substance:	BI 655130 (spesolimab)
Pharmaceutical formulation:	Solution for injection
Source:	Boehringer Ingelheim Pharma GmbH & Co KG
Unit strength:	██████ /prefilled syringe 2mL (150mg/mL)
Posology:	██████ every █ weeks, including at Visit 1 for subjects who were on spesolimab in the parent trial. An increase in dose at W██ to █████ mg █. every █ █████ if needed; Refer to Table 3.1: 1 .
Method and route of administration:	████

Table 4.1.1: 2 Test product 2 – BI matching placebo solution for injection

Substance:	Placebo matching BI 655130 (spesolimab)
Pharmaceutical formulation:	Solution for injection
Source:	Boehringer Ingelheim Pharma GmbH & Co KG
Unit strength:	placebo, █████ prefilled syringe
Posology:	Placebo matching █████ at Visit 1 only for subjects who were on placebo in the parent trial
Method and route of administration:	████

Table 4.1.1: 3 Test product 3 – BI 655130 (spesolimab) solution for infusion

Substance:	BI 655130 (spesolimab)
Pharmaceutical formulation:	██████████
Source:	Boehringer Ingelheim Pharma GmbH & Co KG
Unit strength:	██████████
Posology:	██████████ Visit 1 only for subjects who were on placebo in the parent trial (Loading Dose)
Method and route of administration:	████

Table 4.1.1: 4 Test product 4 – BI matching placebo solution for infusion

Substance:	Placebo matching to BI 655130 (spesolimab)
Pharmaceutical formulation:	██████████
Source:	Boehringer Ingelheim Pharma GmbH & Co KG
Unit strength:	Placebo ██████████
Posology:	Placebo matching ██████████ in Visit 1 only for subjects who were on spesolimab in the parent trial
Method and route of administration:	████

4.1.2 Selection of doses in the trial and dose modifications

In the 1368-0052 PoCC trial, a fixed rather than weight-based dose regimen was selected. Early trials of therapeutic monoclonal antibodies often investigate bodyweight-based regimens to reduce the inter-subject variability in drug exposure. However, there is generally only a modest contribution of body weight to the overall PK and PD variability of monoclonal antibodies. Furthermore, monoclonal antibodies are highly target specific and offer a relatively large therapeutic window compared to new chemical entities. Therefore, most monoclonal antibodies are approved at fixed doses in antibody/target excess in order to cover target turnover and maximize efficacy [R10-6267; R13-4749; R13-4753; R13-4750; R13-4754].

In this extension trial, patients from the active arm in the parent trial will be given [REDACTED] every [REDACTED], which is half the dose of the 1368-0052 PoCC trial. This is to evaluate whether these patients would be able to sustain efficacy at a lower dose. Patients who were in the placebo arm will be given a [REDACTED] dose of spesolimab, followed by [REDACTED] every [REDACTED]. The rationale is to give an opportunity to the patients from the placebo arm to be given active treatment and also to understand induction response after a placebo period. Additionally, this dose was also selected to evaluate efficacy of [REDACTED] dose. All the patients will be reassessed at Week [REDACTED] to evaluate the response and will have the option of either continuing the same dose or increasing the dose.

Data from the 1368-0052 PoCC trial will not be available prior to the 1st patient rolling over into this extension trial. When new data from the PoCC trial becomes available, the impact for this extension trial will be evaluated and if needed the dose would then be adjusted by amending this protocol.

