3. DESCRIPTION OF DESIGN AND TRIAL POPULATION

3.1 OVERALL TRIAL DESIGN

This open label, single-arm, multi-regimen, 2-year extension study investigates the long-term safety and efficacy of spesolimab in patients with HS who have completed their treatment in the 1368-0052 PoCC trial. BI trial 1368-0052 is the first trial from which patients will rollover into this extension trial. Patients rolling over into this trial must have completed the treatment period as required in the 1368-0052 PoCC trial. Ideally, the end of treatment (EoT) visit of the preceding trial is the baseline visit (V1) of this extension trial.

This extension trial consists of a [REDACTED] weeks treatment period followed by a [REDACTED] week safety follow-up period.

Approximately [REDACTED] patients from the 1368-0052 PoCC trial are planned to be rolled over into this open-label extension study.

Patients from the placebo arm of the 1368-0052 PoCC trial will be given an initial [REDACTED] dose of spesolimab plus [REDACTED] placebo, followed by [REDACTED] spesolimab [REDACTED] every [REDACTED] weeks [REDACTED]). Patients from the active arm of the 1368-0052 PoCC trial will be given an initial [REDACTED] placebo plus [REDACTED] spesolimab [REDACTED], followed by [REDACTED] spesolimab [REDACTED] every [REDACTED]. Administration of trial medication at Visit 1 is blinded. See [Section 3.1.1](#) for more details.

[figure not shown]
At Week [REDACTED] of this extension trial, all patients will be assessed for the change of HS-PGA grade. The change in HS-PGA grade will be compared with the assessment at baseline of this extension trial / Week [REDACTED] of the 1368-0052 PoCC trial. Based on the individual responder status decisions on further dosing will be taken as depicted in [Table 3.1: 1](#).

Table 3.1: 1 Week 12 Dose Modification Management

Baseline	Assessment at Week 12	Management
Status from Week 12 of 1368-0052 PoCC trial	HS-PGA grade change from baseline HS-PGA grade of this trial	
Responder (Achieved HiSCR 50)	No change or improvement in grade (i.e., reduction by at least 1 grade)	Continue the same dose
	Worsening in grade (i.e., increase by at least 1 grade)	Option to increase the dose to [REDACTED]
Partial Responder (Achieved HiSCR 25 but did not achieve HiSCR 50)	Improvement in grade	Continue the same dose
	No change or worsening in grade	Increase the dose to [REDACTED]
Non-responder (Did not achieve HiSCR 25)	Improvement in grade	Continue the same dose

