7.1 NULL AND ALTERNATIVE HYPOTHESES

Given the single arm and open-label nature of this trial, no hypothesis testing will be performed in the confirmatory sense. All statistical assessments will be performed in an explorative manner to better understand the efficacy and safety profile of spesolimab.

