7.2.3 Secondary endpoint analyses

For binary endpoints, the efficacy data will be presented over time based on SAF where any data collected after the use of rescue therapy will be censored and then imputed using the Non Response Imputation (NRI) method as described in [Section 7.3](#).

For continuous endpoints, the efficacy data will be presented over time based on SAF where any data collected after the use of rescue therapy will be censored and then may be handled by a mixed effect model for repeated measurements (MMRM).

Further, it is also of interest to explore week 12 efficacy performance of patients who were responders, partial responders and non-responders in the 1368-0052 trial respectively as defined in [Table 3.1: 1](#).

Further details will be provided in the TSAP.

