7.5 DETERMINATION OF SAMPLE SIZE

Given the descriptive nature of this trial, no sample size calculation has been performed. The sample size of this OLE is determined based on the sample size of the preceding parent trial (1368-0052).

8. INFORMED CONSENT, TRIAL RECORDS, DATA PROTECTION, PUBLICATION POLICY, AND ADMINISTRATIVE STRUCTURE

The trial will be carried out in compliance with the protocol, the ethical principles laid down in the Declaration of Helsinki, in accordance with the ICH-GCP, relevant BI Standard Operating Procedures (SOPs), the EU directive 2001/20/EC / EU regulation 536/2014 and other relevant regulations. Investigators and site staff must adhere to these principles. Deviation from the protocol, the principles of ICH-GCP or applicable regulations as will be treated as “protocol deviation”.

Standard medical care (prophylactic, diagnostic and therapeutic procedures) remains the responsibility of the treating physician of the patient.

The investigator will inform the sponsor immediately of any urgent safety measures taken to protect the trial patients against any immediate hazard, as well as of any serious breaches of the protocol or of ICH-GCP.

The BI transparency and publication policy can be found on the following web page: trials.boehringer-ingelheim.com. The rights of the investigator and of the sponsor with regard to publication of the results of this trial are described in the investigator contract. As a rule, no trial results should be published prior to finalisation of the Clinical Trial Report.

The certificate of insurance cover is made available to the investigator and the patients, and is stored in the ISF.

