7.6.3 Other analysis

Since there's dose modification at week [REDACTED] and re-assessment week [REDACTED] according to the Table 3.1: 1 in CTP, descriptive summaries for the status of HS-PGA grade change at Week [REDACTED] and Week [REDACTED] by responder status at baseline will be provided.

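### The question whether efficacy is sustained on half the dose is specified by rollover responder class for HS-PGA only; HiSCR retention among prior-spesolimab responders should be a named output

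*Protocol*

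**What the plan says.** **Protocol.** Section 3.2 says the trial is to "evaluate the sustainability of response". Section 4.1.2 explains why patients from the active arm get half the parent-trial dose: "This is to evaluate whether these patients would be able to sustain efficacy at a lower dose".

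Table 3.1: 1 (Section 3.1) defines response at rollover from Week 12 of the parent trial. Its top row begins "Responder (Achieved HiSCR 50", and a lower HiSCR threshold separates partial responders from non-responders.

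Section 7.2.3 adds that "it is also of interest to explore week 12 efficacy performance of patients who were responders, partial responders and non-responders in the 1368-0052 trial". It names no endpoints, does not cross class with prior arm, and defers details to the SAP.

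**SAP.**
- Section 4 carries the protocol's analyses forward apart from listed adaptations. None of those concerns the responder-class analysis.
- Section 5 measures efficacy change from the parent-trial baseline in the prior-spesolimab arm and from this trial's baseline in the prior-placebo arm.
- Section 6.1 displays results by prior treatment and splits each prior arm into up-titrated patients and a group labelled Other.
- Section 7.5.2 specifies descriptive summaries and line plots for the secondary endpoints and names no responder-class split.
- Section 7.6.3 specifies, by responder status, "descriptive summaries for the status of HS-PGA grade change" at two visits. The public text specifies no other output by class.

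**The concern.** Only a patient who has a response at rollover can sustain it, so the question in 4.1.2 is about what happens to those patients. A HiSCR percentage for the whole prior-spesolimab arm counts a kept response and a new one alike, because both are measured from the parent baseline. If some responders lose HiSCR on the lower dose while others reach it for the first time, the curve can stay flat.

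The one by-class output uses a different measure. HiSCR requires at least a halving of the AN count without a rise in abscesses or draining fistulas (Protocol 5.1.1). HS-PGA is a global grade that also takes in non-inflammatory nodules (5.1.3), and Table 3.1: 1 takes its change from this trial's baseline. The documents do not show that an unchanged grade means HiSCR is kept.

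SAP Section 3 plans an interim analysis once all patients reach Week 12, partly to guide further development. A flat arm-level curve could then be read as efficacy held on half the dose. This applies before any Week 12 dose increase. Also, because 7.2.3 does not cross class with prior arm, patients who responded to placebo could be pooled with those who responded to spesolimab.

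**Working it through.** The plan gives no figure to reproduce: "no sample size calculation has been performed" (Protocol 7.5). The check is how far an arm-level HiSCR percentage determines the share of rollover responders who kept their response.

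**Inputs**
- Total size: "The maximum number of patients eligible to rollover is approximately 45 from multiple countries and multiple sites" (Protocol 3.3). The split by prior arm is not given. *Assumption:* 22, 30 or 34 prior-spesolimab patients, roughly 1/2, 2/3 or 3/4 of 45.
- Share of the arm with HiSCR at rollover, r: not given. *Assumption:* 0.42, 0.50 or 0.59, spanning the 42% to 59% that Protocol 1.1 quotes for adalimumab.

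**Identity.** Let p be the share with HiSCR at Week 12, s the share of rollover responders who kept it, and g the share of the others who gained it. Then

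p = r·s + (1 − r)·g, with g between 0 and 1,

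so s lies between max(0, (p − (1 − r))/r) and min(1, p/r).

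**Flat curve, p = r.** The lower bound becomes max(0, (2r − 1)/r) and the upper bound is 1.
- r = 0.42 or 0.50: s can be 0% to 100%.
- r = 0.59: (1.18 − 1)/0.59 = 0.31, so 31% to 100%.

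In whole patients at 59%, the lower bound is 4/13 = 31% (n = 22), 6/18 = 33% (n = 30) and 6/20 = 30% (n = 34).

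**How extreme those bounds are.** For s = 0 with a flat curve, g must equal r/(1 − r). That is 0.42/0.58 = 72% at r = 0.42 and 100% at r = 0.50. These are mathematical limits, not expected results.

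**Less extreme cases.** Assume n = 30, with 15 responders at rollover and 15 at Week 12. The arm shows 15/30 = 50% in every row.

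| Kept | Newly gained | Share kept | Exact 95% CI for share kept |
|---|---|---|---|
| 15/15 | 0/15 | 100% | 78% to 100% |
| 12/15 | 3/15 | 80% | 52% to 96% |
| 9/15 | 6/15 | 60% | 32% to 84% |
| 8/15 | 7/15 | 53% | 27% to 79% |

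**Precision of a direct estimate** at about 80% kept (Clopper-Pearson): 7/9 gives 40% to 97%, 12/15 gives 52% to 96%, and 16/20 gives 56% to 94%.

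**Does the up-titration split help?** Under Table 3.1: 1 the up-titrated group can hold responders who worsened together with partial and non-responders who did not improve. Other can hold stable responders with improving non-responders. Both groups mix rollover classes and are formed by the Week 12 outcome, so neither isolates retention.

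**The case against.** The strongest reply is that the analysis is already planned. Protocol 7.2.3 commits to Week 12 efficacy by class, SAP Section 4 carries protocol analyses forward, and 7.6.3 does not call itself the only by-class output. This stands as far as it goes. A reader might infer that the by-class analysis was dropped, or that the sustained proportion cannot be obtained, and the documents support neither. What remains is that no visible text names the endpoints, the measure of retention or the crossing with prior arm.

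Second, the public SAP is incomplete. Its contents skip Sections 5.3, 5.4, 6.5 and 10, and Protocol 7.2.4, which the SAP cites, is not shown. Relevant text may be there, so absence from the whole plan cannot be asserted.

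Third, 7.6.3 gives a within-responder result that late responders cannot offset, and SAP Section 7 lists individual values for about 45 patients. Both points hold. Loss of response is not invisible, but it is shown by class only on a measure that does not define rollover response. A count made from listings is not a specified result.

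Fourth, 4.1.2 speaks of the active-arm patients and defines no retention endpoint. That is fair: reading *sustain* as keeping HiSCR is an interpretation, though one consistent with how Table 3.1: 1 defines response.

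Fifth, retention at Week 12 is not a clean test of the lower dose. With a half-life of about 4 weeks (Protocol 1.2.1), 12 weeks is three half-lives. About 1/8 of the drug present at rollover would remain if kinetics were linear, and the residual effect period is 16 weeks (1.2.3). This stands and belongs in the interpretation.

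**Conclusion.** The point holds as a specification gap on a secondary aim. The visible SAP turns the responder-class analysis of Protocol 7.2.3 into HS-PGA grade change only. HiSCR, AN count, draining fistula count and IHS4 are specified by prior arm and up-titration subgroup, and SAP Section 4 does not list this narrowing as a change. Arm-level HiSCR from the parent baseline cannot separate kept from newly gained response: in the assumed example, 50% at both times fits 15/15 or 8/15 kept.

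The mechanism is arithmetic and needs no assumption. Its size rests on an assumed arm size and rollover response rate. The 0% to 100% range should not be read as likely, since it needs 72% to 100% of the other patients to gain HiSCR on the lower dose.

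The matter is worth correcting but not critical. The primary endpoint is safety and "no hypothesis testing will be performed in the confirmatory sense" (Protocol 7.1).

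**What to change.** In SAP 7.6.3, carry out the Protocol 7.2.3 analysis within each prior-treatment arm, by rollover class (responder, partial responder, non-responder) and by visit to Week 12:
- HiSCR, AN count, draining fistula count and IHS4, with the parent baseline for prior spesolimab as in SAP Section 5.
- For prior spesolimab, counts of sustained, lost and newly gained HiSCR.
- As the direct answer to Protocol 4.1.2, the proportion of prior-spesolimab rollover responders still meeting HiSCR at Week 12, with an exact 95% CI. Apply the non-response imputation that SAP Table 6.4: 1 assigns to binary endpoints, so that all rollover responders stay in the denominator.
- Prior-placebo results shown separately, since class there reflects response to placebo and the efficacy baseline is reset.

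Label the output descriptive. State that intervals will be wide and that early visits may still carry exposure from the parent-trial dose. If text in the non-public sections already covers this, a cross-reference from 7.6.3 is enough.

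The cost is SAP wording and a few tables. Lesion counts are scheduled at each visit in the flow chart up to Week 12, and 7.6.3 already uses the class variable, so no new data, visits or change in conduct are needed.
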